### 5.2.3 Subject Exclusion Criteria

The subject must be excluded from participating in the trial if the subject:

1. Is currently participating and receiving study therapy or has participated in a study of an investigational agent and received study therapy or used an investigational device within 4 weeks of the first dose of treatment.
2. Has a diagnosis of immunodeficiency or is receiving systemic steroid therapy or any other form of immunosuppressive therapy within 7 days prior to the first dose of trial treatment.
3. Has a known history of active TB (Bacillus Tuberculosis)
4. Has hypersensitivity to pembrolizumab or any of its excipients.
5. The number of prior therapies is restricted as follows:

Zero or one prior therapies during the preceding one year. This serves to limit the treatment cohort to patients with either only slowly progressive disease, or up to one prior therapy.

No prior PD-1 or PD-L1 antibody therapies are allowed, as in #16

Prior IL-2 is allowed, if it finished more than 1 year prior.

The following are not counted as medical therapies: nephrectomy, radiation therapy, other energy-ablative techniques, or metastasectomy.

6. Has had a prior anti-cancer monoclonal antibody (mAb) within 4 weeks prior to study Day 1 or who has not recovered (*i.e.*,  $\leq$  Grade 1 or at baseline) from adverse events due to agents administered more than 4 weeks earlier.
7. Has had prior chemotherapy, targeted small molecule therapy, or radiation therapy within 2 weeks prior to study Day 1 or who has not recovered (*i.e.*,  $\leq$  Grade 1 or at baseline) from adverse events due to a previously administered agent.
  - Note: Subjects with  $\leq$  Grade 2 neuropathy are an exception to this criterion and may qualify for the study.
  - Note: If subject received major surgery, they must have recovered adequately from the toxicity and/or complications from the intervention prior to starting therapy.

8. Has a known additional malignancy that is progressing or requires active treatment. Exceptions include basal cell carcinoma of the skin or squamous cell carcinoma of the skin that has undergone potentially curative therapy or in situ cervical cancer.
9. Has known active central nervous system (CNS) metastases and/or carcinomatous meningitis. Subjects with previously treated brain metastases may participate provided they are stable (without evidence of progression by imaging for at least four weeks prior to the first dose of trial treatment and any neurologic symptoms have returned to baseline), have no evidence of new or enlarging brain metastases, and are not using steroids for at least 7 days prior to trial treatment. This exception does not include carcinomatous meningitis which is excluded regardless of clinical stability.
10. Has active autoimmune disease that has required systemic treatment in the past 2 years (*i.e.* with use of disease modifying agents, corticosteroids or immunosuppressive drugs). Replacement therapy (*e.g.*.. thyroxine, insulin, or physiologic corticosteroid replacement therapy for adrenal or pituitary insufficiency, etc.) is not considered a form of systemic treatment that would be exclusionary.
11. Has known history of, or any evidence of active, non-infectious pneumonitis.
12. Has an active infection requiring systemic therapy.
13. Has a history or current evidence of any condition, therapy, or laboratory abnormality that might confound the results of the trial, interfere with the subject's participation for the full duration of the trial, or is not in the best interest of the subject to participate, in the opinion of the treating investigator.
14. Has known psychiatric or substance abuse disorders that would interfere with cooperation with the requirements of the trial.
15. Is pregnant or breastfeeding, or expecting to conceive or father children within the projected duration of the trial, starting with the pre-screening or screening visit through 120 days after the last dose of trial treatment.
16. Has received prior therapy with an anti-PD-1, anti-PD-L1, or anti-PD-L2 agent.
17. Has a known history of Human Immunodeficiency Virus (HIV) (HIV 1/2 antibodies).
18. Has known active Hepatitis B (*e.g.*, HBsAg reactive) or Hepatitis C (*e.g.*, HCV RNA [qualitative] is detected).
19. Has received a live vaccine within 30 days of planned start of study therapy.

*Note: Seasonal influenza vaccines for injection are generally inactivated flu vaccines and are allowed; however intranasal influenza vaccines (e.g., Flu-Mist®) are live attenuated vaccines, and are not allowed*

20. Myocardial infarction, stroke, coronary artery bypass surgery, coronary stent, or unstable angina within one year are excluded.

*Note: A subject may enroll in the study and have a start date set in the near future in a way that meets the timelines for exclusion items by the treatment start date*

## 5.2 Trial Treatments

The treatment to be used in this trial is outlined below in Table 2

Table 2 Trial Treatment

| Drug          | Dose/Potency                              | Dose Frequency | Route of Administration                | Regimen/Treatment Period                                                                                                                                                     | Use          |
|---------------|-------------------------------------------|----------------|----------------------------------------|------------------------------------------------------------------------------------------------------------------------------------------------------------------------------|--------------|
| Pembrolizumab | 200 mg                                    | Q3W            | IV infusion outpatient                 | Every 21d ± 3d                                                                                                                                                               | Experimental |
| Interleukin-2 | 15 minute infusion of 600,000 IU/kg/dose* | q8h x5         | IV infusion over 15 minutes, inpatient | Two courses set after corresponding pembrolizumab that defines day 1 of the cycle with intervals of:
P → W1: 2-9 days, usually 7 days
W1 → W2: 6-9 days usually 7 days | Standard     |

\*actual body weight; capped at 66 million IU/dose for subjects > 110 kg.  
P = date of pembrolizumab dose  
W1 = date of first IL-2 dose of the course  
W2 = date of first IL-2 dose of the next course

Trial treatment should begin as close as practical to the date on which eligibility is established and treatment level is allocated (for those patients on the part of the trial where the pembrolizumab dose is still not fixed).

## **5.2.1 Dose Selection/Modification**

### **5.2.1.1 Dose Selection**

The rationale for selection of the 200 mg/dose flat dose to be used in this trial is provided in Section 4.0 – Background and Rationale.

Details on preparation and administration of pembrolizumab (MK-3475) are provided in the Pharmacy Manual.

### **5.2.1.2 Dose Modification**

Adverse events (both non-serious and serious) associated with pembrolizumab exposure may represent an immunologic etiology. These adverse events may occur shortly after the first dose or several months after the last dose of treatment. Pembrolizumab must be withheld for pembrolizumab-related toxicities and severe or life-threatening AEs as per Table 3 below. See Section 5.6.1 and Events of Clinical Interest Guidance Document for supportive care guidelines, including use of corticosteroids.

In general, dose modifications of pembrolizumab are not required for events that appear to be directly related to interleukin-2 treatment and have resolved to a grade that is assessed as safe by the principle investigator, at the time of the next planned pembrolizumab treatment.

Table 3  
Dose Modification Guidelines for Drug-Related Adverse Events

| Toxicity                                                 | Hold Treatment For Grade | Timing for Restarting Treatment                                                                                                     | Discontinue Subject                                                                                                                                                |
|----------------------------------------------------------|--------------------------|-------------------------------------------------------------------------------------------------------------------------------------|--------------------------------------------------------------------------------------------------------------------------------------------------------------------|
| Diarrhea/Colitis                                         | 2-3                      | Toxicity resolves to Grade 0-1.                                                                                                     | Toxicity does not resolve within 12 weeks of last dose or inability to reduce corticosteroid to 10 mg or less of prednisone or equivalent per day within 12 weeks. |
|                                                          | 4                        | Permanently discontinue                                                                                                             | Permanently discontinue                                                                                                                                            |
| AST, ALT, or Increased Bilirubin                         | 2                        | Toxicity resolves to Grade 0-1                                                                                                      | Toxicity does not resolve within 12 weeks of last dose.                                                                                                            |
|                                                          | 3-4                      | Permanently discontinue (see exception below)                                                                           | Permanently discontinue                                                                                                                                            |
| Type 1 diabetes mellitus (if new onset) or Hyperglycemia | T1DM or 3-4              | Hold pembrolizumab for new onset Type 1 diabetes mellitus or Grade 3-4 hyperglycemia associated with evidence of beta cell failure. | Resume pembrolizumab when patients are clinically and metabolically stable.                                                                                        |
| Hypophysitis                                             | 2-3                      | Toxicity resolves to Grade 0-1                                                                                                      | Toxicity does not resolve within 12 weeks of last dose or inability to reduce corticosteroid to 10 mg or less of prednisone or equivalent per day within 12 weeks. |
|                                                          | 4                        | Permanently discontinue                                                                                                             | Permanently discontinue                                                                                                                                            |
| Hyperthyroidism                                          | 3                        | Toxicity resolves to Grade 0-1                                                                                                      | Toxicity does not resolve within 12 weeks of last dose or inability to reduce corticosteroid to 10 mg or less of prednisone or equivalent per day within 12 weeks. |
|                                                          | 4                        | Permanently discontinue                                                                                                             | Permanently discontinue                                                                                                                                            |
| Hypothyroidism                                           | 2-4                      | Therapy with pembrolizumab can be continued while treatment for the thyroid disorder is instituted                                  | Therapy with pembrolizumab can be continued while treatment for the thyroid disorder is instituted.                                                                |
| Infusion Reaction                                        | 3-4                      | Permanently discontinue                                                                                                             | Permanently discontinue                                                                                                                                            |
| Pneumonitis                                              | 2                        | Toxicity resolves to Grade 0-1                                                                                                      | Toxicity does not resolve within 12 weeks of last dose or inability to reduce corticosteroid to 10 mg or less of prednisone or equivalent per day within 12 weeks. |
|                                                          | 3-4                      | Permanently discontinue                                                                                                             | Permanently discontinue                                                                                                                                            |
| Renal Failure or Nephritis                               | 2                        | Toxicity resolves to Grade 0-1                                                                                                      | Toxicity does not resolve within 12 weeks of last dose or inability to reduce corticosteroid to 10 mg or less of prednisone or equivalent per day within 12 weeks. |
|                                                          | 3-4                      | Permanently discontinue                                                                                                             | Permanently discontinue                                                                                                                                            |
| All Other Drug-Related Toxicity              | 3 or Severe              | Toxicity resolves to Grade 0-1                                                                                                      | Toxicity does not resolve within 12 weeks of last dose or inability to reduce corticosteroid to 10 mg or less of prednisone or equivalent per day within 12 weeks. |
|                                                          | 4                        | Permanently discontinue                                                                                                             | Permanently discontinue                                                                                                                                            |

**Note: Permanently discontinue for any severe or Grade 3 drug-related AE that recurs or any life-threatening event.**

 For patients with liver metastasis who begin treatment with Grade 2 AST or ALT, if AST or ALT increases by greater than or equal to 50% relative to baseline and lasts for at least 1 week then patients should be discontinued.

 Patients with intolerable or persistent Grade 2 drug-related AE may hold study medication at physician discretion. Permanently discontinue study drug for persistent Grade 2 adverse reactions for which treatment with study drug has been held, that do not recover to Grade 0-1 within 12 weeks of the last dose.

Dosing interruptions are permitted in the case of medical / surgical events or logistical reasons not related to study therapy (e.g., elective surgery, unrelated medical events, patient vacation, and/or holidays). Subjects should be placed back on study therapy within 3 weeks

of the scheduled interruption, unless otherwise discussed with the Sponsor. The reason for interruption should be documented in the patient's study record.

*Note: These evaluations should be done in relation to each pembrolizumab dose. Adverse events that occur or are noted in between scheduled pembrolizumab infusions, but are within 2 weeks after IL-2 administration and appear to meet Table 3 criteria, and have resolved at the point of the next pembrolizumab dose, and are attributed to the IL-2 treatment's acute side effects do not count as events that are required to be managed as indicated in Table 3. For example, grade 3 creatinine elevation that resolved after the IL-2 was finished but before the next pembrolizumab infusion would not count as an AE that requires interruption of the pembrolizumab treatment schedule.*

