#### 5.2.4 IL-2 treatment checklist, before each IL-2 dose.

Note: This list does not supersede the treating physician judgment on whether to withhold a dose or not.

Lab results – refer to most recent results, generally fewer than 28 hours old.

- a. No current use of steroids or other anti-immune treatments prescribed for management of autoimmune problems. (Use of glucocorticoids for patients who are hypoadrenal is allowed).
- b. No Grade 2 or worse ongoing pembrolizumab-attributed events (Table 6b).
- c. Patient willingness to take another IL-2 dose – query nausea, motivation.
- d. Not requiring oxygen supplement 2L/min or less for oxygen saturation of 90% or more.
- e. Most recent creatinine level should be:
  - a. under 150% of baseline value to start a course
  - b. under 250% of baseline at most recent evaluation for later doses in the same course. (see note on physician judgment)
- f. Systolic blood pressure above target level:
  - a. i. Target = 80 mmHg if baseline was <100
  - b. ii. Target = 85 mmHg if baseline was 100-120
  - c. iii. Target = 90 mmHg if baseline was 120+ mmHg systolic
- g. If atrial fibrillation is present—treating physician evaluation on per-case basis.
- h. Heart rate not documented as continuously 120 for more than 1 hour (during prior 8 hours).
- i. Dopamine off, or less than or equal to 2 mcg/kg/min.
- j. Urine output > 150 ml over last 8 hours.
- k. Two or fewer 500 ml NS bolus had been required in last 8 hours for treating blood pressure or urine output.
- l. Electrolytes and liver function tests should be reviewed by treating physician.

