|                           | Grade 4                                                                                                                                                                                                                                                                                                                                                                                                                                                                                                                                                                                                                                                                                                                                                                                                                                                                                                                                                                                                      | Life threatening consequences; urgent intervention indicated.                                                                                                                                                                                            |

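### Two of the four endocrine rows in Table 3 let pembrolizumab continue or resume where the Note under the table requires permanent discontinuation, and no text says which governs

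*Combined protocol and SAP*

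**What the plan says.** Section 5.2.1.2 governs pembrolizumab. Its lead-in requires the drug to be withheld for pembrolizumab-related toxicities and for severe or life-threatening events, as set out in Table 3.

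Table 3 has four endocrine rows:

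- **Hypothyroidism, Grade 2-4.** Both action columns carry the same text: "Therapy with pembrolizumab can be continued while treatment for the thyroid disorder is instituted".
- **Type 1 diabetes or hyperglycemia (new diabetes, or Grade 3-4).** "Hold pembrolizumab for new onset Type 1 diabetes mellitus or Grade 3-4 hyperglycemia associated with evidence of beta cell failure". The last column, headed as the one for discontinuing the subject, reads: "Resume pembrolizumab when patients are clinically and metabolically stable".
- **Hypophysitis, Grade 4.** "Permanently discontinue".
- **Hyperthyroidism, Grade 4.** "Permanently discontinue".

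The Note directly under the table applies to drug-related events generally and exempts no row: "Permanently discontinue for any severe or Grade 3 drug-related AE that recurs or any life-threatening event". Table 6b (section 7.3.4) describes Grade 4 as "Life threatening consequences; urgent intervention indicated".

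Section 5.7.1, under the thyroid heading, adds a note to the entry for Grade 2 hyperthyroidism and Grade 2-4 hypothyroidism. It leaves stopping or continuing pembrolizumab to the treating physician.

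The IL-2 checklist in section 5.2.4 is separate and applies before each IL-2 dose. Item (b) reads "No Grade 2 or worse ongoing pembrolizumab-attributed events (Table 6b)". Item (a) restricts steroids, with the exception "Use of glucocorticoids for patients who are hypoadrenal is allowed". The checklist's header says that it does not override physician judgment.

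**The concern.** For Grade 4 hypothyroidism or Grade 4 hyperglycemia, an investigator who follows the row and one who follows the Note give the same patient different pembrolizumab treatment, and both can cite Table 3. For hypothyroidism, section 5.7.1 adds a third answer. Section 5.9 refers back to section 5.2.1.2 for the adverse experiences that require a subject to be discontinued, so the ambiguity carries over to trial discontinuation.

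Patient safety comes first, but the data are affected too. The choice of rule decides how many pembrolizumab doses a patient receives. Six doses are required for the dose-delivery definition in section 4.4.4.1, for secondary objective (2) in section 3.3, and for the combination threshold population in Figure 7. If the event falls in block 1, the rule may also decide whether the patient reaches IL-2, and so whether the patient enters the combination treatment population on which section 8.4 bases the response rate.

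**Working it through.** The main check is a comparison of texts. The plan states no figure to reproduce.

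**Step 1. Does the Note reach Grade 4?** It names life-threatening events, and Table 6b describes Grade 4 in those terms. It also names a severe or Grade 3 drug-related event that recurs.

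**Step 2. Rows against the Note.**

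| Endocrine row | Row at Grade 4 | Note at Grade 4 | Agree? |
|---|---|---|---|
| Hypothyroidism (2-4) | may continue | stop permanently | No |
| T1DM/hyperglycemia (T1DM or 3-4) | hold, then resume | stop permanently | No |
| Hypophysitis | stop permanently | stop permanently | Yes |
| Hyperthyroidism | stop permanently | stop permanently | Yes |

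Two of four rows conflict. The recurrence limb raises the same question in those two rows for a second Grade 3 episode. Neither row mentions recurrence, while the Note requires permanent discontinuation.

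**Step 3. Is there a stated exception?** The AST/ALT/bilirubin row points to a numbered footnote for its exception, so the table marks an exception when one is intended. The two endocrine rows carry no such marker. The italic note that closes section 5.2.1.2 exempts only events attributed to acute IL-2 effects, arising within 2 weeks after IL-2 and resolved by the next pembrolizumab dose. It does not cover an endocrine event attributed to pembrolizumab.

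**Step 4. Other text on the same decision.** The lead-in's requirement to withhold does not fit continuing through Grade 4 hypothyroidism. The discretion note in section 5.7.1 fits neither the Note nor the lead-in.

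**Step 5. Where the data could move.**

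- *Dose count.* Pembrolizumab is planned at weeks 1, 4 and 7 of each 9-week block, so without extra cycles dose 6 falls 5 × 3 = 15 weeks after dose 1. A permanent stop in those 15 weeks leaves the patient below six doses. Continuing or resuming need not.
- *Weight of one patient.* 1/24 = 4.2% of the planned evaluable number.
- *DLT count.* Section 8.5 already lists events of Grade 3 or higher after the IL-2 dates as DLTs, apart from typical IL-2 events that have resolved. A Grade 4 endocrine event after IL-2 is therefore normally counted whichever pembrolizumab rule is applied.

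**The case against.** **Precedence can be inferred.** A specific row might be taken to override a general note. Alternatively, the mandatory Note might be taken to override a row that says only that therapy can continue. Both are ordinary ways to read such a table, but they give opposite answers and the protocol adopts neither. The second also fails for diabetes/hyperglycemia, where the row is itself phrased as a direction.

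**Life-threatening is not identical to Grade 4.** The seriousness section of Table 6b defines life-threatening separately, as immediate risk of death in the investigator's view. New Type 1 diabetes is listed without a grade, so resuming after it conflicts with the Note only if that case was life-threatening, or was a recurrent severe or Grade 3 event. This stands and narrows the point. It does not remove the conflict at Grade 4, where Table 6b's own grade description uses the same term.

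**Stronger readings that the documents do not support.**

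- *That the IL-2 checklist gives the opposite instruction to Table 3.* It governs a different drug, covers only pembrolizumab-attributed events and defers to physician judgment. The Subject Replacement Strategy expressly foresees pembrolizumab without IL-2 for patients who no longer meet IL-2 criteria at B2W2.
- *That checklist items (a) and (b) contradict each other.* They are separate conditions that can both apply. Exclusion criterion 10 admits patients already on physiologic steroid replacement, so item (a) has a use apart from pembrolizumab toxicity.
- *That the ambiguity inflates DLT stopping.* Suppose a fraction q of IL-2-treated patients are counted as DLTs only because item (b) ended their IL-2, independently of a 15% background. The counted rate is 1 − 0.85(1 − q), which is 19.25%, 23.5% and 27.75% at q = 5%, 10% and 15%. The exact probability of crossing the Figure 9 boundary within 24 patients is then 0.124, 0.252 and 0.416, against 0.047 at q = 0. These are illustrative upper readings. The values of q are assumed. The documents do not say that replaced endocrine disease stays Grade 2 or worse, and no text turns repeated item (b) holds into permanent discontinuation. Nor do the figures measure the Grade 4 conflict.

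What remains of the checklist issue is a gap in definition: whether an endocrine event controlled on replacement is still ongoing at Grade 2 or worse.

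**Conclusion.** The point holds for two rows, hypothyroidism and Type 1 diabetes/hyperglycemia. At Grade 4 the row and the Note cannot both be followed. The same uncertainty arises for a recurrent Grade 3 event in those rows, and the lead-in and the section 5.7.1 note do not resolve it. It does not extend to hypophysitis or hyperthyroidism.

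The conclusion rests on Table 6b's description of Grade 4 and on the absence of any precedence statement. The number of patients affected cannot be estimated, because the documents give no rate of Grade 4 or recurrent Grade 3 endocrine events. The statistical effect is on pembrolizumab dose counts and population membership. The effect on DLT counts is limited for the reason in step 5. It is worth correcting because it concerns a safety instruction and the correction is cheap.

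**What to change.** The sponsor and medical monitors should reconcile five places: the Table 3 Note, the hypothyroidism row, the Type 1 diabetes/hyperglycemia row, the lead-in to Table 3, and the thyroid note in section 5.7.1. Each Grade 4 or recurrent Grade 3 endocrine event should lead to one pembrolizumab instruction, with any exception marked as the hepatic one is. Which rule applies is their clinical decision.

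As a secondary clarification, state whether an endocrine event controlled on replacement counts as ongoing Grade 2 or worse under checklist item (b). Then state in section 8.5 whether IL-2 withheld solely for that reason counts as a DLT.

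The cost is an amendment of a few sentences, with no new procedures or patients.
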